# 2 Outcomes and other variables

# 2.1 Primary Outcome

#### 2.1.1 Definition and Derivation of Primary Outcome

The primary outcome is the frequency of moderate to severe exacerbation (defined as requiring treatment with systemic corticosteroids and/or antibiotics in the community of hospital or hospitalisation) in the 48 weeks. COPD exacerbations is defined by symptomatic worsening of COPD requiring:

- Use of systemic corticosteroids for at least 3 days; a single depot injectable dose of corticosteroids will be considered equivalent to a 3-day course of systemic corticosteroids;
  - and/or
- Use of antibiotics; and/or
- An inpatient hospitalisation or death due to COPD

The total number of moderate to severe exacerbation over 48 weeks is defined as a count outcome. This will be derived using the number of moderate to severe exacerbations each participant had over the course of 48 weeks. The outcome will have a minimum value of zero.

Maximum study time for a patient is approximately 49 weeks (48 weeks + 7 days); defined as the time from randomisation to the date of visit 13 (week 48). This will be calculated; (visit-13 date – randomisation date + 1).

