7.10 Withdrawal criteria

The only specified withdrawal criteria for this study will be for participants that miss more than one dose of the study treatment, or who delay a scheduled study visit for >4 weeks. These participants will remain in follow-up for the trial duration. If a participant wishes to completely withdraw from the study, or is withdrawn for reasons other than a missed or delayed dose, the research team will encourage them to undertake the 'withdrawal visit' procedures and assessments which will signify the end of their participation. This will include participants who withdraw via telephone. It will be at the participant's discretion whether or not they attend the withdrawal visit. Withdrawal visits should be completed as soon as possible, however the timeframe will be largely dependent on what the participants finds acceptable.

Every effort should be made by the research team to keep the participants in the trial. However, participants have the right to withdraw their consent to take part in the trial at any time without having to give a reason and this will not affect their future care. Withdrawal details and reasons (if known) should be recorded on the withdrawal/loss to follow up CRF and in the medical notes. In addition, the investigator may discontinue a participant from the trial at any time if the investigator considers it necessary. The IMP will also be discontinued in the case of an adverse event which the investigator considers sufficient to jeopardise the safety of the trial participant. Participants who want to discontinue protocolled treatment should be encouraged to remain in the trial and continue to be followed-up as per protocol or as of routine care.

Every effort should be made to keep the participant in the trial to collect important efficacy and safety data. Withdrawals from the trial should be discussed with the CI or their deputy and the Trial Manager. If a participant has withdrawn from the trial for any reason, then his/her screening and participant ID number(s) cannot be issued to another participant.

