Loss to follow-up will be minimised by diligent liaison with the participant, their medical team and if required the general practitioner. If a participant fails to attend the clinic for trial visit, the research team should contact the participant and re-schedule the missed visit within a week. If the participant can't be contacted or misses his/her next appointment, the research team should make every effort to contact the participant again by phone and letter. If the participant still cannot be contacted, then he/she can be withdrawn from the trial and the reason in the notes and eCRF can be recorded as 'lost to follow-up'.

A participant will be considered to have completed the trial if:

- they continue to take trial treatment until Visit 12 (Week 44) and attend Visit 14 (Week 60)
- they continue to participate in the trial until Visit 13 (Week 48) regardless of whether they continue to take IP.

As stated in section 3.3.2, participants will undergo a non-contrast CT scan at the beginning and end of the trial. Bearing in mind the average age of participants, diagnosis of COPD and smoking history, lung nodules are a very common finding in this population. Therefore participants will remain in the trial whilst they are followed up in the virtual nodule clinic, however

at the point where a suspicious nodule has led them into the cancer pathway, they will be withdrawn from the trial.

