8.6 Dosage schedules

See figure 1 for dosing schedule. In animal trial and phase I human studies both, intravenous and subcutaneous (SC) routes were used, with no significant difference in safety. For ease of administration we will be using the SC route in this trial. The drug dose is fixed at 490mg every 4 weeks for 12 visits.

A window of up to 4 weeks will be allowed within which a participant will be able to delay or miss taking a scheduled dose. A delay will then be carried through to all their subsequent study visits. If the participant misses a dose it will be recorded in the notes and the next scheduled dose will be administered. Participants will be allowed to miss a single dose of the study drug (See Section 7.7) and are permitted up to a 4 week treatment delay.

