8.10 Trial restrictions

There is no scope in this study for dose reduction of the IMP, however participants are permitted to miss a single dose. The dose for the patients' standard of care therapy(s) for COPD will be maintained where possible, however this will be left up to the clinician's discretion. The clinician will also have discretion to alter any concomitant medication(s) that are unrelated to their COPD as required.

Participants are required to complete the scheduled clinic visits within the time windows allowed in the protocol. As the administration of trial medication is only at the clinic, and the need to maintain the required intervals between dosing, it is very important to adhere to the time windows for each visit.

All study visits have been given a window of +/- 7days to allow for flexibility, apart from visit 14 which will have a window of +/- 14 days. Any visits completed outside of this window will be logged as protocol deviations. Participants will be permitted where required, up to a 4 week treatment delay of a scheduled dosing visit, to allow for adverse events, holidays or other unexpected events. The participant can miss a dose and receive their next dose at the scheduled visit, or they can receive a delayed dose when available and their subsequent visit schedule would be altered accordingly to incorporate the delay (see Section 8.6). Depending on the nature of the AE/SAE it will be left to the clinician's discretion to determine if the patient should be withdrawn from the study. Participants that are delayed more than 4 weeks (more than a single dose) will be withdrawn.

Persistent deviations would indicate potential non-compliance and will have to be discussed with the Chief Investigator and the Sponsor regarding possible withdrawal. Those participants who are planning to take more than a 4 week consecutive holiday would not be included in the study, this will be asked at screening.

Participants should be compliant in taking their daily COPD medications during the course of the trial. Dose and regimen of routine medications should not be changed during the course of the trial (screening, treatment, and follow-up periods) except for treatment of an exacerbation or unless absolutely medically necessary. Baseline treatment should be maintained at the same dose and regimen at it was at the time of entry to the trial.

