# **3** Analysis Sets/Populations

#### 3.1 Protocol deviations

#### 3.1.1 Major deviations

Protocol deviations that will affect inclusion in trial populations are:

- Participants found to be ineligible after randomisation
- Participants who receive the wrong study treatment
- Participants who miss greater than one dose of study treatment
- Participants who delay a scheduled study visit greater than 4 weeks

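### Does the SAP's study-time formula leave the primary rate model without a sound denominator for delayed or early-leaving participants?

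*SAP*

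**What the plan says.** SAP 2.1.1 derives the primary outcome from "the number of moderate to severe exacerbations each participant had over the course of 48 weeks". It then says: "Maximum study time for a patient is approximately 49 weeks (48 weeks + 7 days"), and describes this time as "defined as the time from randomisation to the date of visit 13 (week 48). This will be calculated" with visit-13 date minus randomisation date plus 1.

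The protocol lets visits slip. Section 8.10 permits "up to a 4 week treatment delay of a scheduled dosing visit", and section 8.6 adds: "A delay will then be carried through to all their subsequent study visits". SAP 3.1.2 treats delays under 4 weeks as minor deviations with no effect on the analysis sets. SAP 3.1.1 lists as a major deviation "Participants who delay a scheduled study visit greater than 4 weeks". Protocol 7.10 says of participants beyond the dose or delay limits: "These participants will remain in follow-up for the trial duration".

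Some participants leave before visit 13. On lung nodules, protocol 7.10 says that "at the point where a suspicious nodule has led them into the cancer pathway, they will be withdrawn from the trial".

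SAP 3.2 defines intention-to-treat as everyone randomised and keeps the data of early withdrawals up to the point where they leave the study. SAP 5.4.1 fits a negative binomial model with the log of time on study as offset, and uses all observed data with no deletion or imputation. Its next sentence explains the offset as allowing for differing time on treatment.

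**The concern.** Exposure time is the denominator of the only primary analysis, so its definition should leave no room for choice. On a first reading it leaves three openings.

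- **The maximum.** A carried 4-week delay takes visit 13 past 49 weeks. If events were counted for 48 weeks only but divided by a longer time, delayed participants' rates would be understated. An imbalance in delays between arms would then bias the rate ratio.
- **No visit 13.** After death, full withdrawal or loss to follow-up there is no visit-13 date to put in the formula. A program with a missing offset would drop these participants, contrary to intention-to-treat.
- **Two names for the offset.** Time on study and time on treatment differ for participants who stop the drug and stay in follow-up. Protocol 7.10 counts them as completers at visit 13.

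Two analysts could in principle produce two different primary rate ratios.

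**Working it through.** **Inputs.** From the documents: a 48-week period, a visit window of 7 days either way, a permitted delay of up to 4 weeks, 80 participants (40 per arm), 10% drop-out, over-dispersion 1.3 (taken as the negative binomial dispersion k), and placebo rates of 2 or 2.5 a year with reductions of 50% or 40%. The shares of participants delayed, leaving or stopping drug are assumptions, since the documents give none by arm.

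**1. The stated maximum.** 48 x 7 + 7 = 343 days = 49.0 weeks; with the formula's + 1, 344 days. The figure reproduces when there is no delay.

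**2. With a carried 4-week delay.** 336 + 28 + 1 = 365 days (week 52). Adding the 7-day window gives 372 days (week 53), and 372 - 344 = 28 days above the stated maximum. This is not a firm ceiling. The documents do not say whether the 4 weeks applies per visit or in total. Protocol 8.11 and SAP 2.5 allow a missed dose to be given within 1 week, and those passages must be reconciled with protocol 8.6 and 8.10.

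**3. Does the 49 weeks enter the analysis?** No. The offset is the log of the actual days to visit 13, so a participant seen on the delayed date contributes log(365). The 49-week figure truncates nothing.

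**4. Size if count and time did not match.** Suppose the count stops at week 48 (337 days by the formula) and time runs on.

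- Per delayed participant: 337/365 = 0.923 (7.7% too low) and 337/372 = 0.906 (9.4% too low).
- Per arm, with share p delayed to day 372, the mean rate is multiplied by 1 - p x 0.094. For p = 10% this is 0.9906; for p = 30% it is 0.9718.
- Rate ratio with 10% of placebo and 30% of active delayed: 0.9718/0.9906 = 0.981. The reverse split gives 1.019.

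Large-sample negative binomial fits (k = 1.3, both sample-size scenarios, count to day 336) agree:

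| Reading | Shares, placebo v active | Rate ratio multiplied by |
|---|---|---|
| Count and time both to visit 13 | all splits tried | 0.999 to 1.001 |
| Count to day 336, time to day 372 | 10% v 10% | 1.000 |
| Same | 10% v 30% | 0.980 |
| Same | 30% v 10% | 1.020 |

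**5. No visit 13.** At the planned drop-out this is at most 10% x 80 = 8 participants, if all leave before week 48. A visit 13 held by telephone under the COVID-19 provisions still has a date. With exits spread evenly over days 28 to 336 and unrelated to exacerbations, matched windows give the same ratio whether time ends at the last visit or at exit. If events are known only to the last 4-weekly visit but time runs to exit, the ratio is multiplied by 1.001 (10% v 10%), 0.994 (5% v 15%) or 1.008 (15% v 5%).

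**6. Offset taken as time on treatment.** With 28 days per dose received, stops spread evenly over doses 1 to 11, and a 48-week count, the multipliers are 0.980 to 0.985 (10% v 10%), 1.069 to 1.087 (10% v 20%) and 0.879 to 0.881 (20% v 10%). If stops come only after 6 to 11 doses, the range is 0.958 to 1.038.

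**7. Against sampling error.** Var(log RR) = [(1/t)(1/r0 + 1/r1) + 2k]/n, with t = 48/52 = 0.923 and n = 40 per arm.

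- Rates 2 v 1: (1.625 + 2.6)/40 = 0.1056, SE 0.325.
- Rates 2.5 v 1.5: (1.156 + 2.6)/40 = 0.0939, SE 0.306.

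A 2% shift is 0.020/0.306, or about 0.07 SE. The extreme in step 6 is 0.129/0.306, or about 0.4 SE.

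**The case for a change.** The strongest case for a change is that a primary denominator should be written down, not inferred. A death due to COPD counts as a primary event, so a participant who dies of COPD in week 20 contributes an event with no exposure written for it. The withdrawal column of the visit schedule appears unmarked in the exacerbation row, so the last date of known status may differ from the exit date. The offset slip sits in the primary model's own paragraph. A few sentences would settle all this.

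The textual points stand: the 49 weeks is too low if delays carry through, no end date is written out for early leavers, and one phrase in SAP 5.4.1 is loose. The inference that the analysis is at risk does not.

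- The sentence in SAP 2.1.1 is about the maximum, so its formula reads naturally as full follow-up time, not as a rule that excludes those with less.
- For those with less, SAP 3.2 names the stopping point (study discontinuation) and SAP 5.4.1 forbids deletion. An offset that allows for differing lengths of follow-up is there mainly for such people. Death ends observation in the same way.
- Both documents call the 48 weeks the treatment period, so time on treatment can be read as time within that period. The term placed in the model is time on study.
- No passage says that the count stops at day 336 while time runs to a later visit 13.

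A rewrite also carries a risk. Ending exposure at the last date on which exacerbation status was known could place the end at the exacerbation contact itself, which would inflate that person's rate. It would also depart from the stopping point in SAP 3.2.

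**Conclusion.** No change to the plan follows. The 49-week maximum is a descriptive slip that enters no calculation. The missing end date is a gap that an analyst following SAP 3.2 and 5.4.1 fills sensibly, with study discontinuation or death. The second name for the offset is loose wording beside a correctly named term.

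The expected effect on the rate ratio is nil when count and time share a window, and about 2% at most on the mismatched reading with 10% against 30% fully delayed. That is under a tenth of a standard error. The larger multipliers, 0.88 to 1.09, need the less likely reading of the offset together with assumed, unequal shares stopping drug. Even then the extreme is about 0.4 of a standard error. All of these figures rest on assumed shares, on exits unrelated to exacerbations, and on 1.3 being the negative binomial dispersion.

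This SAP version also follows database lock and a draft analysis report (Revision History, version 2.1). Redefining exposure now would add a post-lock edit to the primary derivation for no gain. The statistical report is the natural place to state the end date that was used.

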### 2.1.2 Hypothesis to be investigated

COPD patients treated with anti-ST2 therapy will have reduced COPD exacerbation frequency after 48 weeks treatment compared to placebo treated patients.

### 2.2 Secondary Outcomes

#### 2.2.1 Definition and Derivation of Secondary Outcomes

**Note:** \* indicates this data is held on Macro database; ^ indicates this data is held externally to the Macro database and will be provided by the team at NIHR Leicester Biomedical Research Centre – Respiratory.

The secondary endpoints/outcomes are:

#### 1. Safety and tolerability (All visits)

- AE event rate in the 48 weeks of the trial from first dose\*
- SAE event rate in the 48 weeks of the trial from first dose\*

#### 2. Patient related outcomes (PROs) (Weeks 0, 4, 12, 24, 36 and 48)\*

- St George's Respiratory Questionnaire for COPD patients (SGRQ-c)
  - Total score\*
  - Domains (*post hoc*):
    - i. Symptoms score^
    - ii. Activity score^
    - iii. Impacts score^
- COPD Assessment Test (CAT)
- mMRC Dyspnoea Scale
- Visual analogue score (VAS)
  - o Total
  - o Dyspnoea
  - o Cough
  - Sputum production
- Sputum purulence colour card

#### 3. Lung function (Weeks 0 and 48)

- Pre and post BD Spirometry\*
  - o FEV1
  - FEV1 % predicted
  - o FVC
  - o FEV1/FVC %
  - BD reversibility %
- Whole body plethysmography (body box)\*
  - o TLC
  - o RV
  - o RV/TLC %

#### 4. Inflammation (Weeks 0, 4, 12, 24, 36, 48)

- Cell count
  - Blood inflammatory cell differentials\*
    - WBC
    - Eosinophils
    - Neutrophils
  - Sputum inflammatory cell differentials
    - Eosinophils
    - Neutrophils
    - Macrophages
    - Lymphocytes
    - Epilthelial cells
    - Total

# 2.2.2 Hypotheses to be investigated

All secondary outcomes measures are hypothesised to benefit from the anti-ST2 intervention.

## 2.3 Exploratory Outcomes

#### 2.3.1 Definition and Derivation of Exploratory Outcomes

- Quantitative measures of airway geometry and densitometry Contrast thoracic CT-derived outcomes (Weeks 0 and 48)
  - MLD E/I (small airway)
  - o % WA
  - LA (Larger airways)
- Mediators
  - Sputum mediator profiling (biomarkers)
  - o Blood biomarkers
- Cell subset analysis including but not restricted to exploration of ILC2 cells
- Urine biomarkers of inflammation
- Mediator profiling (biomarkers)
- Upper airway inflammation:
  - o nasosorption
  - o nasal epithelial sampling (optional)
- Airway infection and ecology:
  - targeted qPCR (bacteria and viruses) for common airway pathogens
  - o microbiomics
- Breath volatile organic compound (VOC) profiling (PTRMS and ADVION) breathomics
- Pharmacogenomics response analysis in subgroups determined by SNPs for alleles associated with the IL33/ST2 axis

### 2.4 Subgroups and/or interactions

There will be a subgroup analysis of the primary outcome, rate of protocol-defined moderate to severe COPD exacerbations through 48 weeks treatment period and secondary outcomes SGRQ-C and FEV1 by baseline blood eosinophil count (dichotomised about median value).

### 2.5 Treatment Compliance

All doses of the trial treatment will be administered subcutaneously (SC) at the research site by blinded research staff. The prescribed dosage, and mode of administration should not be changed. If a participant misses a dose, the missed dose can be given within 1 week. Any changes from the intended regimen will be recorded in the CRF.

A summary of the treatment received will be provided by treatment arms. This will include information in terms of dosing, administration, changes and delays from Visit 1

ST-QRD-1 v2

(week 0) to Visit 13 (week 48). Any treatment compliance will be presented by treatment arm and deviations from protocol including loss to follow-up, withdrawal by clinician and withdrawal of consent will be included.

# **3** Analysis Sets/Populations

#### 3.1 Protocol deviations

#### 3.1.1 Major deviations

Protocol deviations that will affect inclusion in trial populations are:

- Participants found to be ineligible after randomisation
- Participants who receive the wrong study treatment
- Participants who miss greater than one dose of study treatment
- Participants who delay a scheduled study visit greater than 4 weeks

#### 3.1.2 Minor deviations

All other (non-major) protocol deviations will be reported but will not affect analysis populations. e.g. Missing one dose of study treatment, visit assessments delays less than 4 weeks, visit assessments earlier than scheduled (refer to Table 2 in Appendix 1).

### 3.2 Intention-to-treat Population

The intention-to-treat population will be comprised all the participants randomised in to the trial (regardless of whether they received trial drug) analysed in their allocated group, outcome data obtained from all participants will be included in the data analysis (i.e regardless of study completion or data completeness). All data up to the time of study discontinuation will be included for participants who withdrew prematurely.

### 3.3 Modified intention-to-treat population

The modified intention-to-treat will be comprised all the participants randomised to the trial (regardless of whether they received trial drug), analysed in their allocated group, where data is available. Therefore participants with missing outcome data will be excluded from the analysis (i.e complete case analysis). No imputation will be carried out for the missing data.

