# 5.5 Secondary Outcome Analyses

### 5.5.1 Primary Analysis of Secondary Outcomes

All secondary end-points will be analysed using the modified intention-to-treat population, with the exception of adverse events, for which we will analyse the safety population, consisting of all participants who received at least one dose of trial medication.

Descriptive statistics of all the secondary outcomes listed in section 2.2 will be presented by treatment arms and overall by assessment time points (i.e by visit). Numbers (with percentages) for binary and categorical variables and means (and standard deviations), and medians (with lower and upper quartiles) for continuous variables will be presented.

All binary secondary outcomes will be compared between treatment groups using logistic regression. Odd ratio (OR) with two-side 95% CI and P-value will be reported for those outcomes.

All continuous longitudinal outcomes (repeated measurements i.e week 0, 4, 12, 24, 36 and 48) will be compared using mixed effects model with explanatory variables of treatment arm, number of exacerbations in the 12 months prior to the trial (stratification factor), visit number in weeks (categorical) and patient identification as a random effect to account for repeated measures over time. This method will able to handle missing data happening during the follow-up measurements. Adjusted mean differences alongside two sided 95% CI and P-value will be reported for these outcomes. If the distribution of the variable found to be far from normal distribution, a log transformation will be used to modify the non-normality. Adjusted geometric mean difference alongside two sided 95% CI and P-value will be reported.

To compare change from baseline to 48 weeks (pre and post treatment measurements), analysis of covariance (ANCOVA) model with baseline value as a covariate will be used. Adjusted mean differences with 95% confidence interval will be reported if the data are normally distributed. If there is severe departure from normality the first approach will be data transformation with the above technique applied to the transformed data. Adjusted geometric mean difference with 95% CI and P-value will be reported. If the data cannot be transformed to normality then the Mann-Whitney U test will be used and in this case no baseline adjustment will be made.

All safety data will be analysed as described in section 7 of this SAP.

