# 6.1 Subgroup Analyses

A subgroup analysis of the primary outcome will be carried out based on baseline blood eosinophil, dichotomised by the median value. The primary outcome of COPD exacerbations in 48 weeks will be summarised by low or high eosinophil count and analysed as described in section 5.4.1. An indicator variable to specify the eosinophil group (low or high) will be added to the analysis model. The additional of an interaction term between eosinophil indicator variable and treatment group will assess the difference in treatment efficacy between low and high eosinophil groups. *Post hoc* the clinically important eosinophil cut-off (>300 eosinophils/ $\mu$ L) was included as an additional subgroup analysis.

Additional subgroup analyses of the SGRQ-C and FEV1 will also be carried out based on the baseline blood eosinophil, dichotomised by the median value. The SGRQ-C sore and FEV1 will be summarised by low or high eosinophil count and analysed as described in section 5.4.1. An indicator variable to specify the eosinophil group (low or high) will be added to the analysis model. The addition of an interaction term between eosinophil indicator variable and treatment group will assess the difference in SGRQ-C score and FEV1 between the low and high eosinophil groups.

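### SAP 3.3 excludes participants with missing outcome data from secondary analyses whose mixed model is meant to handle missing visits, and SAP 6.1 sends FEV1 and SGRQ-C to the count model

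*SAP*

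**What the plan says.** **Population.** SAP 3.3 defines the modified ITT set as randomised participants "analysed in their allocated group, where data is available", then adds: "Therefore participants with missing outcome data will be excluded from the analysis (i.e complete case analysis". It allows no imputation. SAP 5.5.1 states: "All secondary end-points will be analysed using the modified intention-to-treat population", with adverse events the only exception.

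**Models.** SAP 5.5.1 gives two routes for continuous outcomes. The first: "All continuous longitudinal outcomes (repeated measurements i.e week 0, 4, 12, 24, 36 and 48) will be compared using mixed effects model", with arm, stratification factor and visit as explanatory variables and a random participant effect. Of this model it says: "This method will able to handle missing data happening during the follow-up measurements". The second, for change from baseline to week 48: "analysis of covariance (ANCOVA) model with baseline value as a covariate will be used". Neither sentence names an outcome. SAP 2.2.1 gives the questionnaires and cell counts the six-visit list, and heads the spirometry and body box items "Lung function (Weeks 0 and 48"; protocol 3.5.2 uses the same two weeks for lung function.

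**Subgroups.** SAP 6.1 says that SGRQ-C and FEV1 "will be summarised by low or high eosinophil count and analysed as described in section 5.4.1". Section 5.4.1 is the negative binomial model for exacerbation counts, with log time on study as offset.

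**Context.** In the schedule (SAP 1.3), the questionnaires, blood count, sputum sample and both spirometry rows carry the footnote suspending them at weeks 48 and 60 during COVID-19 restrictions. SAP 5.5.2 makes post-bronchodilator FEV1, SGRQ-C and CAT the key secondary outcomes. SAP 5.5.3 plans no sensitivity analysis for any secondary outcome.

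**The concern.** A mixed model can only handle missing follow-up if participants with missing follow-up are in it. If 3.3 is applied first, at participant level, everyone with a gap has already gone, and the sentence about the model in 5.5.1 has nothing to act on. It would also set aside protocol 10.11, which calls for intention to treat for each efficacy outcome, using the outcome data of all participants.

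The pointer in 6.1 adds a second problem. A count model with a time offset and a rate ratio does not suit a questionnaire score or a lung volume. Taken at its word, it would also bring in the ITT population of 5.4.1, so the SGRQ-C subgroup analysis would rest on a different set of participants from the main SGRQ-C analysis.

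Two analysts could follow this SAP faithfully and report different participants and different models for SGRQ-C, and different models for the FEV1 subgroups. Protocol 10.6 has the secondary outcomes reported mainly as estimates with confidence intervals, so lost precision would show directly in interval width.

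**Working it through.** **1. The passages side by side.** SAP 3.2 defines an ITT set that is explicit about including participants whatever their completeness, and 5.4.1 analyses all observed data without deleting or imputing any. SAP 3.3 creates a separate set whose distinguishing feature is exclusion for missing data. The literal reading is therefore credible. SAP 3.3 and 5.5.1 agree only if the exclusion is applied per observation, or only to participants with no usable value; the SAP does not say so.

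**2. Inputs for the size.** From the documents: 80 randomised and 10% drop-out (SAP 1.2.4), so 80 × 0.9 = 72; five post-baseline visits (weeks 4, 12, 24, 36, 48). Assumed, because the documents give neither: the share *m* of participants without week 48 (20, 40, 60%, unrelated to arm) and the within-participant correlation *ρ* (0.5 to 0.9).

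**3. Literal exclusion.** Only 72(1 − *m*) participants remain, and the standard error (SE) of the arm effect is multiplied by 1/√(1 − *m*).

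**4. Partial data kept.** In a random-intercept model with an arm main effect, a participant with *k* visits carries information proportional to 1/(*ρ* + (1 − *ρ*)/*k*). At *ρ* = 0.5 this is 1/0.6 = 1.667 for five visits and 1/0.625 = 1.600 for four. At *m* = 60% the average is 0.4 × 1.667 + 0.6 × 1.600 = 1.627, and the SE factor is √(1.667/1.627) = 1.012.

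| *m* | Remaining of 72, literal | SE factor, literal | SE factor, partial kept, *ρ* = 0.5 | *ρ* = 0.9 |
|---|---|---|---|---|
| 20% | 58 | 1.118 | 1.004 | 1.001 |
| 40% | 43 | 1.291 | 1.008 | 1.001 |
| 60% | 29 | 1.581 | 1.012 | 1.002 |

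SAP 5.5.1 counts week 0 among the repeated measurements. With six and five visits in place of five and four, the largest factor falls to √(1.714/1.686) = 1.008, so the conclusion is the same.

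At *m* = 40%, 29 of 72 participants lack week 48. Literal exclusion would then discard their 29 × 4 = 116 observed values, out of 72 × 5 − 29 = 331, or 35%.

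**5. No COVID-19 loss at all.** With an assumed 5% missing independently at each of five visits, 1 − 0.95⁵ = 0.226, so 23% of participants would still be excluded, although 95% of the values exist.

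**6. FEV1.** The two-week heading in SAP 2.2.1 fits the ANCOVA and not the six-visit mixed model. Post-bronchodilator spirometry is also scheduled at weeks 4, 12, 24 and 36, and on this reading enters no between-arm comparison. What it could add was simulated (12,000 runs per cell, 36 per arm, week-48 loss of 20/40/60%), comparing repeated measures having an estimated unstructured covariance with a completer ANCOVA. The week-48 SE is 2–3/5–7/5–7% smaller with equal correlations of 0.7–0.9, and 6–7/12–15/17–20% smaller with correlations of 0.8–0.9 per 12 weeks that decay with time. With no week-48 loss there is no gain.

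**The case against.** The strongest reply is that 3.3 is loosely worded and need not be read against the rest of the plan. Its own words "analysed in their allocated group, where data is available" suggest an available-data analysis, 5.5.1 is the more specific text for these models, and protocol 10.11 points the same way. That reading is coherent, and it may be what was intended. It does not remove the exclusion sentence, so the clarification is still needed; but the 12/29/58% figures are the cost of the stricter reading, under assumed losses, and not a prediction.

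A reader might infer that the SAP has no model for FEV1. The documents do not support that: 5.5.1 does not name FEV1, but the two-week heading makes the ANCOVA the natural choice. Nor is leaving interim spirometry out of that ANCOVA an error; it is a consistent prespecified choice, and the gain from using those visits is small if visits are equally correlated.

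A reader might also take the protocol's remark, under amendment SA05, about many missed week-48 CT scans as a measure of lost questionnaires and spirometry. It concerns CT only, and the schedule footnote lets participants complete procedures once restrictions lift.

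It can also be said that an ANCOVA without the stratification factor does not breach protocol 10.9, which keeps non-primary main analyses unadjusted. True, but the 5.5.1 mixed model already adjusts for that factor, so the two documents need aligning in any case.

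**Conclusion.** The wording conflict between SAP 3.3 and 5.5.1 is real, and literal use of 3.3 would discard usable data from the longitudinal secondary outcomes. The 6.1 pointer to 5.4.1 is wrong for continuous outcomes on any reading, and is probably clerical. The FEV1 model is implied but should be stated.

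The cost is precision, of unknown size: 12/29/58% on the SE at assumed week-48 losses of 20/40/60% under the literal reading, against about 1% at most if partial data stay in. This rests on loss unrelated to arm and on a random-intercept model with an arm main effect.

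A reader might infer bias in the secondary results, or a threat to the main result. Neither is shown. A suspension of clinic visits gives no evident reason for loss to differ by arm, and the primary analysis uses the ITT set with all observed data, not the population in 3.3.

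**What to change.** 1. **SAP 3.3:** reword so that participants with at least one post-baseline value stay in the longitudinal models, with all their observed data and no imputation.
2. **SAP 6.1 and 5.5.1:** point each subgroup analysis to its 5.5.1 model (mixed model for SGRQ-C, ANCOVA for FEV1), and state in 5.5.1 that lung function uses the ANCOVA.
3. **ANCOVA and protocol 10.9:** add the randomisation stratification factor to the ANCOVA, as the mixed model already has it, and bring 10.9 into line.

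*Optional:* a supplementary repeated-measures analysis of post-bronchodilator FEV1 at weeks 4 to 48, with baseline, stratum and arm-by-visit terms and a week-48 contrast. Moving FEV1 into the existing mixed model would not serve, because that model has no arm-by-visit term. The supplement relies on data missing at random given earlier visits, and does not help pre-bronchodilator spirometry, reversibility or body box. The ANCOVA keeps precedence.

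**Cost:** a few sentences in the SAP, one in the protocol, some code, and no new data. The SAP revision history places v2.1 after database lock and review of the draft analysis report, and v3.0 follows it. Every change from the analysis already run must therefore be reported as post hoc, beside the result already obtained. Where that analysis already kept partial data and used the 5.5.1 models, items 1 and 2 change wording only.
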